# Primary outcome analysis – favourable 6-month GOSE score

#### ITT analysis

The binary primary outcome of favourable GOSE (scores 5-8) will be compared between treatment groups using a risk ratio together with a 95% confidence interval and p-value, estimated by a log-binomial regression model. If model convergence is not achieved, then Poisson regression with robust standard errors will be applied. Supplementary analyses will adjust for the randomisation stratification variables of country/state and GCS<9 as fixed effects in the regression model. These analyses will use the 6 month GOSE regardless of the actual duration at the time of measurement. The number of patients with 6 months GOSE assessed prior to 4 months or beyond 8 months will be tabulated, and sensitivity analyses excluding these patients will be performed.

If the proportion of patients missing the primary 6 month GOSE outcome exceeds 5%, a supplementary analysis using multiple imputation of the missing outcomes using chained equations will be employed using relevant baseline and postbaseline variables in the imputation models that are predictive of GOSE, or of GOSE being missing, and constructed separately for each treatment arm. Patients who withdrew consent for any data to be used will not be included in these imputations. This multiple imputation analysis will be regarded as supplementary.

Post hoc sensitivity analyses will make adjustment for any variables exhibiting substantial imbalance across treatment arms at baseline.

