## Randomisation

Trial packs are prepared by an independent pharmaceutical packaging company with either TXA or placebo. Packs are consecutively numbered, opaque, foil parcels with a tamper proof seal. Upon confirmation of eligibility, patients are randomised (1:1) to TXA or placebo, with the randomisation stratified by state and country participating in the study, and additionally by the presence of severe traumatic brain injury (TBI) defined by a Glasgow Coma Scale (GCS) <9 assessed at the time of randomisation.

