# Sample size

Targeting 90% power to detect an increase in a favourable GOSE outcome (scored 5–8) from 60% to 69% with TXA, this trial would require 592 patients in each arm (1184 total) with a twosided 5% significance level. In a protocol amendment (PATCH Protocol ANZIC-RC/ V.1.6 3 February 2020) accommodation for a 10% loss to follow-up, the required sample size was increased to 658 patients in each arm (1316 total).

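### The principal risk ratio leaves out the randomisation strata, so its confidence interval is conservative if they predict GOSE: a modest, avoidable loss of precision, with no bias

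*SAP*

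**What the plan says.** The Randomisation section describes 1:1 allocation "with the randomisation stratified by state and country participating in the study, and additionally by the presence of severe traumatic brain injury (TBI"), with severe TBI defined as GCS<9 at randomisation.

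General principles makes the ITT analysis the principal one. Under ITT analysis, the primary outcome is compared between arms by a risk ratio from a log-binomial model, with robust Poisson regression if that model fails to converge. No covariate is named for this model. The next step reads: "Supplementary analyses will adjust for the randomisation stratification variables of country/state and GCS<9 as fixed effects in the regression model". The headline estimate, interval and p-value are therefore unadjusted, and the SAP gives no reason for this order.

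The same section ends with a further, separate step: "Post hoc sensitivity analyses will make adjustment for any variables exhibiting substantial imbalance across treatment arms at baseline".

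The Sample size section is based on "Targeting 90% power to detect an increase in a favourable GOSE outcome" "from 60% to 69% with TXA" at a "twosided 5% significance level". It gives "592 patients in each arm (1184 total") and, after allowing for 10% loss to follow-up, 658 per arm.

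**The concern.** Stratified allocation forces the arms to be nearly balanced on GCS<9 and region. This reduces the true sampling variance of the treatment contrast. A model that omits the strata does not know this: its standard error still includes the outcome variation between strata. The reported interval is therefore wider than it should be whenever the strata are prognostic.

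They may well be prognostic here. The outcome is a neurological and functional scale on which death and severe disability both count as unfavourable. The SAP also treats GCS<9 as important enough to be both a stratifier and a planned subgroup.

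What is at stake is the precision of the one principal test. Two prespecified analyses of the same effect will be reported, and the less precise one carries the conclusion. If the result is close to the boundary, the two could fall on opposite sides of 5%.

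**Working it through.** **Inputs from the SAP.** Favourable GOSE 60% versus 69% (RR 0.69/0.60 = 1.15), two-sided 5%, 90% power, 592 per arm, 10% loss (Sample size); 1:1 allocation stratified by state/country and GCS<9 (Randomisation).

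**Assumptions, not in the SAP.** A share q = 40% of patients with GCS<9; a placebo favourable rate lower by d = 10, 20, 30 or 40 points in that stratum, averaging 60% overall; the same RR in both strata. Region is left out of the closed-form steps.

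**Step 1: the SAP's own figure.** Pooled-variance formula, mean rate 0.645:

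n = [1.960·√(2·0.645·0.355) + 1.282·√(0.60·0.40 + 0.69·0.31)]² / 0.09² = (1.326 + 0.863)² / 0.0081 ≈ 592 per arm.

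592/0.90 = 657.8, so 658. Both figures reproduce, and they rest on an unstratified comparison.

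**Step 2: under the null (60% in both arms).** The unadjusted SE of log RR is √[2·(0.40/0.60)/592] = 0.0475. The outcome variance is 0.60·0.40 = 0.24. Its between-stratum part is q(1−q)d² = 0.24d², leaving 0.24(1−d²) within strata. Hence SE ratio (unadjusted/true) = 1/√(1−d²), and actual type I error = 2[1 − Φ(1.96 × ratio)].

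**Step 3: at the design effect.** The unadjusted variance is (0.40/0.60 + 0.31/0.69)/592 = 1.1159/592, so SE_u = 0.0434. With a constant RR each arm has a between-stratum part of 0.24d²/0.36 = 0.6667d², so the true variance is (1.1159 − 1.3333d²)/592, with root SE_t. Then:
- unadjusted power = Φ[(ln 1.15 − 1.96·SE_u)/SE_t]
- adjusted power = Φ[ln 1.15/SE_t − 1.96]

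| Gap d | SE excess, null | Type I error, unadjusted | SE_t, design | SE excess, design | Power unadjusted | Power adjusted |
|---|---|---|---|---|---|---|
| 10 | 0.5% | 4.9% | 0.0432 | 0.6% | 89.7% | 89.9% |
| 20 | 2.1% | 4.5% | 0.0424 | 2.5% | 90.2% | 91.0% |
| 30 | 4.8% | 4.0% | 0.0410 | 5.9% | 90.9% | 92.6% |
| 40 | 9.1% | 3.2% | 0.0390 | 11.2% | 91.9% | 94.7% |

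Varying q from 20% to 50% does not change the picture. The smallest loss (q = 20%, d = 10) is 89.7% versus 89.8% power. The largest (q = 50%, d = 40) is 92.0% versus 94.9%, with type I error 3.2%.

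**Step 4: simulation.** 1316 patients, 10% missing, permuted blocks of 4 within six regions by GCS<9, modest regional differences, robust Poisson models, 4000 replicates. Block size and number of regions are assumptions.

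| Gap (q) | Null rejection, unadjusted / adjusted | Power at RR 1.15, unadjusted / adjusted |
|---|---|---|
| 10 (30%) | 4.8% / 4.9% | 90.0% / 90.7% |
| 20 (40%) | 5.0% / 5.4% | 89.6% / 90.7% |
| 30 (40%) | 3.1% / 4.1% | 91.2% / 93.2% |
| 40 (40%) | 3.4% / 4.9% | 91.6% / 95.3% |

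The Monte Carlo error of a 5% rejection rate is √(0.05·0.95/4000) = 0.3 points, so the 10- and 20-point rows show no clear departure from 5%. The 30-point null row ran low for both models. In every row unadjusted rejects less often than adjusted, as expected. The mean estimate was about 1.15 from both models at the design effect.

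**The case against.** The strongest reply is that nothing here is invalid. The sample size was computed for an unstratified comparison, and the unadjusted principal analysis matches it. The planned 90% power is essentially met in every scenario, and in the closed-form results it rises slightly as the strata become more prognostic. The test does not exceed its nominal level and the risk ratio is unchanged. All of this stands. Power is lost only relative to the adjusted analysis that the SAP also plans.

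The size is also uncertain. The SAP gives neither the share of patients with GCS<9 nor outcome rates by stratum, so with a 10-point gap the loss is negligible. This too stands.

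Three stronger readings are tempting, and the SAP does not support them:

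- **That the strata are ignored.** They are not: the adjusted model is prespecified and names both factors. Only its rank is at issue.
- **That power falls by 5 to 13 points.** Losses of that size appear for a smaller effect, RR 1.10, with gaps of 33 to 50 points (57% versus 62%, and 58% versus 71%). The SAP plans for RR 1.15, where the loss over the 10- to 40-point range is about 0 to 3 points.
- **That the imbalance-based adjustment lets the data choose the principal model.** In the ITT analysis it is labelled a post hoc sensitivity analysis, so it cannot alter the headline result.

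**Conclusion.** The point holds as one of efficiency. The principal interval and p-value are conservative to the extent that GCS<9 and region predict 6-month GOSE. There is no bias, and type I error is not inflated.

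Under the assumed 10- to 40-point gaps with 40% GCS<9, the cost is a null standard error about 0.5% to 9% too large and, at the SAP's own effect, about 0 to 3 points of power. In terms of information, the adjusted analysis would need (SE_t/SE_u)² of the unadjusted sample, which is about 99% at a 10-point gap and 81% at a 40-point gap. The direction follows from the design as long as the strata are prognostic. The size rests on assumed stratum rates and a constant RR across strata.

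This is a recommended improvement; the trial's conclusion would be valid without it.

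**What to change.** In the ITT analysis section, swap the two analyses already specified. Make the log-binomial model with country/state and GCS<9 as fixed effects the principal analysis, keep robust Poisson as the stated fallback, and report the unadjusted risk ratio as supplementary. Add a rule, fixed in advance, for pooling state/country levels with few patients. Make the change before treatment codes are opened.

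The cost is SAP wording plus the pooling rule; no new data and no change in sample size are needed. The one small downside is a higher chance that the log-binomial model does not converge with more terms, which the Poisson fallback already covers. Adding further covariates such as age or systolic pressure, or adjusting infrequent binary secondary outcomes for every region, is a separate choice that this fix does not require.

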# STATISTICAL ANALYSES

# **General principles**

The analysis and reporting of the results will follow the CONSORT guidelines. (2) Baseline characteristics will be tabulated by using appropriate summary statistics. Data for the primary outcome will be analysed using the intention-to-treat (ITT) and per protocol (PP) populations (see definitions and details below), with the ITT analysis regarded as the principal analysis. All secondary and tertiary outcomes will be analysed using the intentioe using the ITT population only. A nominal two-tailed 5% significance level will be employed. No adjustment to the 5% level is required for the two interim analyses due to their conservative boundaries having negligible impact on the overall Type I error rate. No correction for multiple testing will be performed.

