#### Per Protocol analysis

The Per Protocol analysis will use the same methods as the ITT analysis, confined to the patients meeting the per protocol population definition. Because the patients not meeting the PP population definition have been excluded, there may no longer be balance in patient characteristics between treatment groups. The baseline characteristics in the TXA and placebo arms will be tabulated and compared for the 'compliant' (PP) patients. Any variables exhibiting imbalance will be adjusted for as covariates in the risk-ratio regression models.

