## Subgroup analyses

Planned sub-group analyses will assess consistency across subgroups of differences between TXA and placebo arms with respect to the primary outcome in the intention to treat population only. These will be assessed using regression models with interaction term(s) between the particular subgroup and treatment arm. These analyses will provide a risk ratio

and confidence interval for the effect of randomised arm in each subgroup and the interaction p-value. The subgroup variables are:

- Age, dichotomised to >= 50 years
- Time from injury to first dose (<1 hour, 1-<2 hours, 2-<3 hours, >=3 hours)\*
- First valid recorded systolic blood pressure categories (<=75, 76–89, >=90 mm Hg)
- Mechanism of trauma (penetrating, blunt, blast/burns\*)
- Baseline GCS<9.

\*If there are <10 patients in any single category then this category will be tabulated but not included in the regression modelling.

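### Beyond country/state and GCS<9, further covariates are chosen only by observed arm imbalance, which gains the ITT sensitivity analysis little and can leave a strong predictor unadjusted in the per-protocol analysis

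*SAP*

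**What the plan says.** The principal analysis is an unadjusted ITT risk ratio for favourable 6-month GOSE. Three further rules govern adjustment.

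- **ITT, supplementary.** The randomisation strata (country/state and GCS<9) enter as fixed effects. This is prespecified.
- **ITT, sensitivity.** "Post hoc sensitivity analyses will make adjustment for any variables exhibiting substantial imbalance across treatment arms at baseline".
- **Per protocol.** The ITT methods are reused, the SAP accepts that balance may be lost, baseline tables are compared, and "Any variables exhibiting imbalance will be adjusted for as covariates in the risk-ratio regression models".

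Neither imbalance rule says which variables are candidates, what size of difference counts, or whether prognosis matters. The ITT rule requires the imbalance to be substantial; the per-protocol rule does not. By contrast, the multiple imputation paragraph of the ITT section does choose variables by whether they predict GOSE or its missingness.

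The per-protocol definition removes, among others, patients who did not receive both doses or who received open-label TXA. Secondary outcome 3 describes the second dose as an 8-hour infusion.

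**The concern.** Whether a baseline variable is worth adjusting for depends mainly on how strongly it predicts outcome. In a randomised comparison, observed imbalance says nothing about that. A screen on imbalance passes over strong predictors that happen to be balanced, and so loses precision. It admits weak predictors that happen not to be balanced.

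The per-protocol analysis has more at stake. A patient who dies or deteriorates before the 8-hour infusion ends can leave the set, so the two arms of the set may differ systematically. Confounding is then roughly imbalance multiplied by prognostic strength, and the rule looks only at the first factor. The estimate could keep confounding by an important predictor although the SAP presents the adjustment as the remedy.

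**Working it through.** **1. Reproduce the design figures.** Inputs from the Sample size section: favourable outcome "from 60% to 69% with TXA", 90% power, two-sided 5%. With pooled variance and mean proportion 0.645:

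n = [1.960·√(2·0.645·0.355) + 1.282·√(0.60·0.40 + 0.69·0.31)]² / 0.09² = 592 per arm.

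592/0.90 = 657.8, so 658 per arm after 10% loss. Both match the SAP. The target is 9 points, a risk ratio of 0.69/0.60 = 1.15.

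**2. How often chance alone flags a variable in ITT.** Assume a cut-off of 0.1 on the standardised difference; the SAP gives none.

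- P(flag) = 2Φ(−0.1/√(2/592)) = 8.5%, or 7.0% at 658 per arm.
- With 15 independent variables (assumed), about 15 × 0.085 = 1.3 are flagged at 592 per arm.
- With a cut-off of 0.2, about 0.01 are flagged.
- With p<0.05 as the trigger, 0.75 are expected, and at least one is flagged with probability 1 − 0.95¹⁵ = 54%.

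The number of covariates therefore depends on a cut-off that the SAP does not state. Which ones are flagged is independent of prognosis.

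**3. Precision in ITT.** Two simulations at 592 per arm and 60% v 69%, flag at 0.1, linear risk-difference models with robust standard errors:

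| Adjustment | A: power | B: power | B: rejection under the null |
|---|---|---|---|
| None | 92% | 90.6% | 4.5% |
| Imbalance-picked | 92–93% | 92.3% | 3.9% |
| GCS + imbalance-picked | 95% | – | – |
| Prespecified prognostic | 97% | 96.9% | 4.2% |

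A: randomisation stratified on GCS, 14 other variables of which two (age, systolic pressure) are prognostic, AUC 0.80–0.82, 3,000 trials at each of two prognostic strengths. B: 15 variables of which three are prognostic, no stratification, 2,000 trials. Because the SAP already prespecifies GCS<9, the closest comparison is 95% against 97%.

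**4. Bias in the per-protocol set.** For a binary predictor, bias in the risk difference = imbalance × outcome gap. For a predictor other than GCS<9, assume a 4-point imbalance:

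| Outcome gap | Bias | Share of 9 points |
|---|---|---|
| 20 points | 0.04 × 0.20 = 0.8 points | 9% |
| 30 points | 0.04 × 0.30 = 1.2 points | 13% |
| 40 points | 0.04 × 0.40 = 1.6 points | 18% |

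At the 30-point gap, a true 69% against 60% would appear as 67.8% or 70.2%, a risk ratio of 1.13 or 1.17 instead of 1.15.

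**5. Can the screen choose the wrong variable?** Assume 400–500 per arm in the per-protocol set, 40% prevalence and a p<0.05 trigger.

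- *Strong predictor* (30% v 80% favourable), 42.5% v 37.5% by arm. p = 0.15 at 400 and 0.11 at 500 per arm, so it is not flagged. Risk ratio bias = (0.425·0.30 + 0.575·0.80)/(0.375·0.30 + 0.625·0.80) = 0.5875/0.6125 = 0.959.
- *Weak predictor* (57% v 62% favourable), 44% v 36% by arm. p = 0.02 and 0.01, so it is flagged. Risk ratio bias = 0.598/0.602 = 0.993.

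The trigger matters: the strong predictor's standardised difference is 0.05/√0.24 = 0.102, so a cut-off of 0.1 would just catch it and 0.2 would not. A 3-point difference (standardised 0.061, bias factor 0.975) escapes all three.

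**The case against.** The case against has real force, and several stronger readings that a reader might draw are not supported.

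- **That all adjusted analyses are chosen after the fact.** They are not. The stratum-adjusted ITT analysis is prespecified, and the imbalance-based one is openly labelled a post hoc sensitivity analysis.
- **That GCS<9 goes uncorrected per protocol.** A 4-point imbalance with a 50-point gap would give 2.0 points, 22% of the target. But the per-protocol section reuses the ITT methods, which plausibly brings in the GCS<9 adjustment as a supplementary model. The exposed variables are the others, such as age or systolic pressure.
- **That the ITT rule mostly adjusts for irrelevant variables.** That share follows from the assumed mix of variables, and the SAP lists none. Only the independence of flag and prognosis can be shown.
- **That the main result or its error rate is compromised.** The principal ITT analysis uses neither rule, and rejection under the null in simulation B was 3.9%.
- **That selection must follow unblinding.** The SAP does not say when imbalance is judged; coded arms could be used, before outcomes are seen.

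It can also be said that the per-protocol rule covers any imbalance, so a modest one would be caught. Read literally, though, almost every variable differs somewhat between arms. Some cut-off must be applied in practice, and none is stated. The simulations also used risk differences, whereas the SAP specifies log-binomial or robust Poisson models, so their power figures are indicative only.

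What remains is that neither rule names covariates or considers prognosis, and that in the per-protocol set this can matter.

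**Conclusion.** The point holds in limited form and is a recommended change, not a threat to the main result. For ITT the cost is modest: about 95% against 97% power in a non-principal analysis under the assumptions of simulation A, plus room for discretion because the threshold is undefined. For the per-protocol analysis of the primary outcome the rule can miss a strong predictor and adjust for a weak one. A plausible size is 0.8 to 1.6 points, 9% to 18% of the design difference, with 1.2 points (13%) as the central illustration. The imbalances, outcome gaps, prevalence, per-protocol size and cut-offs are assumptions; the SAP supplies only the design rates, sample sizes and rules. The conclusion that the screen uses one of the two factors behind confounding does not depend on those figures.

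**What to change.** Before unblinding, replace both imbalance rules with one fixed list of prognostic baseline covariates: age and systolic pressure as continuous variables, mechanism of injury, GCS and country/state. All are already stratification or subgroup variables. The subgroup entry reads "First valid recorded systolic blood pressure categories"; for this use, the SAP should specify a reading taken before the first dose.

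Use the list in the adjusted ITT model and in the per-protocol model whatever imbalance is seen. State in the per-protocol section that the stratification factors are included. Keep the baseline tables for both populations, but report imbalance descriptively only.

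The cost is SAP wording, with no new data. A few missing covariate values will need a simple stated rule, such as simple imputation or a missing-value indicator. If a log-binomial model with continuous covariates fails to converge, the SAP's robust Poisson fallback applies. Baseline adjustment will not remove all selection bias from post-randomisation exclusions, and the SAP should say so where it describes the per-protocol analysis.

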#### Per Protocol analysis

The Per Protocol analysis will use the same methods as the ITT analysis, confined to the patients meeting the per protocol population definition. Because the patients not meeting the PP population definition have been excluded, there may no longer be balance in patient characteristics between treatment groups. The baseline characteristics in the TXA and placebo arms will be tabulated and compared for the 'compliant' (PP) patients. Any variables exhibiting imbalance will be adjusted for as covariates in the risk-ratio regression models.

# Secondary and tertiary endpoint analyses

The binary secondary outcomes of vascular occlusive events (#4), mortality at 24 hours, 28 days and 6 months (#6) and incidence of sepsis to 28 days (#8) will be analysed using the same log-binomial regression modelling approach as the primary outcome. Cumulative mortality to 6 months will also be displayed with Kaplan-Meier curves. Blood product usage (#1) will be dichotomised as any/none and also analysed with log-binomial regression. The quantity of blood product usage among patients receiving the product will be summarised with medians and interquartile ranges, and compared between treatment groups using quantile (median) regression, reporting the difference in medians between treatment arms together with 95% Cls and p values. Analyses of blood lactate concentration (#2) (regardless of assay method) and coagulation profile variables at each time point (#3) will similarly use quantile regression to compare medians between treatment groups. Blood lactate concentration (#2) obtained by venous and arterial samples will each also be dichotomised at >3mmol, and a composite measure of >3mmol for either sampling method will be calculated. INR (#3) will be dichotomised at >1.3 IU, and fibrinogen (#3) at <1 g/L and at <2 g/L. These dichotomised variables will be analysed as binary variables as above. Ventilator-free days in the first 28 days (#5) will assign a value of 0 to patients dying within 28 days regardless of location at time of death, and a value of 28 days if never ventilated in ICU or never admitted to ICU. This will be analysed using quantile regression to estimate the difference in median ventilation-free days. The 4 causes of death (#7a,b,c,d) in patients that died at any time up to 6 months will be tabulated and reported descriptively. The cumulative incidence of each cause of death to 6 months will be displayed graphically taking into account the other competing causes of death, and with cause-specific hazard ratios estimated using Cox regression with censoring at the time of all other causes of death. A composite cause of 'potentially preventable death' will be calculated as any of bleeding, vascular occlusion and multi-organ failure. Comparison of median quality of life outcomes at 6 months (#9) between treatment arms will be analysed using quantile regression, with patients not alive at 6 months treated as having missing values (and see below), and with EQ-5D calculated using Australian weights (3).

Additional analyses of each of the vascular occlusive events (#4) and sepsis (#8) at 28 days will be performed to take into account the competing risk of death. This will use cumulative incidence functions with estimated incidence at 28 days, with the incidence compared across treatment groups using risk ratios with 95% CIs derived using the delta method. For analysis of quality of life outcomes at 6 months, for patients not alive at that time a value of 0 will be imputed for the EuroQol 5-Dimension (EQ5D) summary and VAS scores (3). For the WHODAS scale, in the absence of published guidelines for addressing mortality, a score of 61 will be imputed, placing death as worse than the maximum scale score of 60. These modified quality of life outcomes will also be analysed using quantile regression. Supplementary analyses of these outcomes will use inverse probability of death weighting rather than imputation of values to accommodate truncation by death.

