## Secondary Objectives:

(1) To determine the effect of early administration of TXA, compared to placebo, on coagulation and fibrinolysis, and on clinical outcomes that are mediated through other putative inflammatory, immune, and neurological effects of plasmin.

(2) To determine whether early administration of TXA, compared to placebo, is associated with excessive vascular occlusive events, especially among potentially higher risk patients (e.g., aged >50 years old).

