# Secondary outcomes

- 1. Units of blood products used (packed red blood cells, fresh frozen plasma, platelets, prothrombin complex concentrate, recombinant factor VIIa, cryoprecipitate) in the first 24 hours
- 2. Blood lactate concentration at patient arrival to hospital
- **3.** Coagulation profile (international normalised ratio, activated partial thromboplastin time, fibrinogen, platelet count) at:
  - a. hospital arrival;
  - b. end of treatment with study drug (i.e., immediately after administering the second dose of the study drug by 8-hour infusion);
  - c. 24 hours after the first dose of study drug.
- **4.** Vascular occlusive events (deep venous thrombosis, pulmonary embolism, myocardial infarction, stroke) up until 28 days or hospital discharge (whichever occurs first).
- 5. Ventilator-free days in first 28 days.
- 6. Mortality at:
  - a. 24 hours;
  - b. 28 days;
  - c. 6 months.
- 7. Proportion of deaths due to:
  - a. bleeding;
  - b. vascular occlusion (pulmonary embolus, stroke or acute myocardial infarction);
  - c. multiorgan failure;
  - d. brain/neurological injury.
- **8.** Cumulative incidence of sepsis up until 28 days or hospital discharge (whichever occurs first).
- **9.** Quality of life (World Health Organisation Disability Assessment Schedule (WHODAS) 2.0 and EuroQol 5-Dimension (EQ-5D)) at 6 months.

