# **Analysis Populations**

## A. Intention-To-Treat (ITT) population

The ITT population will consist of all randomised patients.

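### Blood-product quantity is tested only among recipients, a group formed after randomisation, so the difference in medians is not a randomised comparison and can hide or reverse a saving

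*SAP*

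**What the plan says.** The SAP's Secondary outcomes section lists as item 1 "Units of blood products used (packed red blood cells, fresh frozen plasma, platelets" and three further products, in the first 24 hours. It does not limit the outcome to patients who were transfused.

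General principles says secondary outcomes are analysed "using the ITT population only". Under Analysis Populations, "The ITT population will consist of all randomised patients".

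Secondary and tertiary endpoint analyses splits outcome 1 in two:
- **Any use:** "Blood product usage (#1) will be dichotomised as any/none and also analysed with log-binomial regression".
- **Quantity:** "The quantity of blood product usage among patients receiving the product will be summarised with medians and interquartile ranges, and compared between treatment groups". The method is median regression, reporting a difference in medians with 95% CIs and p-values.

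No analysis of units over all randomised patients is described. The additional analyses at the end of that section cover vascular events, sepsis and quality of life, but not blood products.

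**The concern.** Whether a patient receives a product is settled after randomisation. The first secondary objective is "To determine the effect of early administration of TXA, compared to placebo, on coagulation and fibrinolysis", so the plan itself expects TXA to act on the process that leads to transfusion. If TXA spares some patients with small needs any transfusion, those patients leave the TXA recipient group while their counterparts stay in the placebo recipient group. The remaining TXA recipients are then heavier bleeders on average. Early death before transfusion, or longer survival with time to receive more, can also change who is in the subset.

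The difference in medians therefore mixes an effect of TXA with a change in who is compared. It carries a CI and p-value without any caveat. The SAP recognises the hazard elsewhere: its Per Protocol analysis section warns that exclusions may upset balance, and plans covariate adjustment. It also shows an alternative: ventilator-free days are assigned values for patients who die within 28 days or are never ventilated.

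**Working it through.** **Inputs from the SAP.** Outcome 1, the two-part analysis and the ITT definition are as set out above. The only design figure used is 592 per arm (Sample size section). It reproduces:

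n = [1.960·√(2·0.645·0.355) + 1.2816·√(0.60·0.40 + 0.69·0.31)]² / 0.09² = (1.3264 + 0.8634)² / 0.0081 = 592.

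It serves only as a realistic trial size; the point does not depend on it.

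**Assumed inputs.** The SAP gives no transfusion rates, so the distributions below are assumptions and a range is shown.

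**Quantities compared.** With U0 and U1 the units under placebo and TXA, the plan contrasts median(U1 | U1 > 0) with median(U0 | U0 > 0). The sets U1 > 0 and U0 > 0 hold the same kind of patient only if TXA does not affect receipt. The all-randomised contrast is E(U1) against E(U0), with zeros included.

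**Worked case: negative binomial, k = 0.7, mean 5; TXA averts 60% of 1-2 unit transfusions and changes nobody else.**
- P(0) = (0.7/5.7)^0.7 = 0.230, so 77% are transfused. P(1) = 0.141 and P(2) = 0.105.
- Share moved to zero: 0.6 × (0.141 + 0.105) = 0.148. The transfused share falls from 77% to 62%.
- Mean units fall by 0.6 × (1 × 0.141 + 2 × 0.105) = 0.21, from 5.0 to 4.8.
- Placebo recipients: cumulative share 0.429 at 3 units and 0.517 at 4, so the median is 4.
- TXA recipients: 0.491 at 5 units and 0.566 at 6, so the median is 6.

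Average use falls while the planned statistic rises by two units. At 592 per arm, the recipient median was higher on TXA in 91% of 1,000 simulated trials.

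**Range over eight negative binomial settings.** Entries are recipient medians.

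| k / mean | Placebo | One unit less per patient | 60% of 1-2 unit use averted | Mean 30% lower |
|---|---|---|---|---|
| 0.7 / 5 | 4 | 5 | 6 | 3 |
| 0.7 / 3 | 3 | 3 | 4 | 2 |
| 0.3 / 2 | 3 | 3 | 4 | 2 |
| 0.3 / 5 | 5 | 5 | 6 | 4 |
| 1 / 5 | 4 | 4 | 5 | 3 |
| 1.5 / 5 | 4 | 4 | 5 | 3 |
| 2 / 4 | 4 | 3 | 4 | 3 |
| 0.5 / 4 | 4 | 4 | 5 | 3 |

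- One unit less per patient: the recipient median rises in one setting, is unchanged in six and falls in one. Where it is unchanged, the saving is hidden.
- Small transfusions averted: it rises in seven and is unchanged in one.
- Mean 30% lower: it falls in all eight, which is the right direction.

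**A different distribution.** Suppose 50% are never transfused, recipients' units are 1 plus a negative binomial (mean 4.5, median 3), and TXA spares half of those needing 3 units or fewer. Any use falls from 50% to 36.5%, and mean units per randomised patient from 2.25 to 2.01 (about 11% less). The recipient median rises from 3 to 4. At 592 per arm it was higher on TXA in 96% of simulated trials.

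**The case against.** **The any/none analysis would reveal the shift.** It covers all randomised patients. In the worked case the difference is 77% against 62%, with standard error √(0.77·0.23/592 + 0.62·0.38/592) = 0.026, so z is about 5.7. A careful reader would see fewer patients transfused on TXA beside the higher recipient median. This stands and lowers the severity. It does not supply a valid comparison of quantity.

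**This is a small part of the plan.** It is one part of one of nine secondary outcomes, and the primary outcome is untouched. That stands too. A reader might infer that it concerns the trial's main bleeding outcome, but the SAP ranks no secondary outcome above another and also lists death from bleeding and the coagulation profile.

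**The restriction is open.** It stands in the same sentence as the method, so the mismatch with the ITT rule is a disclosed analysis choice. Disclosure does not make the comparison randomised.

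**Reversal depends on the assumptions.** A reader might infer that the result will have the wrong sign. The table does not support that. The averted-transfusion case assumes no benefit in heavier bleeders, and other benefits leave the median unchanged or move it correctly.

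**Zero for every non-recipient has its own flaw.** A patient who dies before transfusion would score the best possible value, so a life-saving drug could appear to increase blood use. This stands, and the fix must deal with it.

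**Conclusion.** The fault is real. The planned difference in median units is confined to a post-randomisation subset that TXA can alter, does not match the SAP's own ITT statement, and has no all-randomised counterpart for quantity. It can hide a saving or give it the wrong sign, but neither is certain. Depending on how TXA acts, the recipient median rose by up to two units, stayed the same, or fell correctly.

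Those sizes rest on assumed transfusion distributions. The structural argument rests only on receipt following randomisation and being open to influence by treatment. The point should be fixed. It is not critical, because the any/none comparison is sound and no primary conclusion depends on this p-value.

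**What to change.** In Secondary and tertiary endpoint analyses:
- Compare units of each product over all randomised patients, counting non-recipients as zero, by a difference or ratio of means with a bootstrap or robust CI. For products used by a minority, a median would be zero in both arms, and a purely rank-based analysis would add little to any/none.
- State how deaths within 24 hours are handled, for example by a sensitivity analysis that ranks early death as the worst outcome.
- Keep the any/none risk ratio.
- Report recipients' medians and interquartile ranges descriptively, with no between-arm CI or p-value.

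The cost is a change of wording and a little more analysis of the same data. The downside is that means are sensitive to a few massive transfusions.
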